4.6.2 Procedures for Subjects Who Discontinue Treatment

Subjects who discontinue from treatment should undergo the Study Completion procedures tabulated in Section 6.1 for the purpose of safety monitoring within 7 days after their last dose of study medication. Any subject that discontinues with ongoing AEs should be followed until resolution of their AE(s) or until the investigator has determined that the AE(s) has stabilized. In addition subjects should be followed up per Table 6-4 off treatment for up to 24 weeks, or when commencing therapy if earlier.

4.6.3 Withdrawal from the Study

A subject will be withdrawn from the study for any of the following reasons:

- Lost to follow up
- Withdrawal of consent
- Death

If a subject is lost to follow up, every reasonable effort must be made by the study-site personnel to contact the subject and determine the reason for discontinuation/withdrawal. The measures taken to follow up must be documented.

When a subject withdraws before completing the study, the reason for withdrawal is to be documented in the eCRF and in the source document. Study drug assigned to the withdrawn subject may not be assigned to another subject. Subjects who withdraw will not be replaced. Subjects who withdraw consent during the treatment or follow-up phase will be offered an optional safety follow-up visit, at which the assessments from the Week 4 follow-up visit need to be performed.

Subjects who withdraw consent from the PK substudy (see Section 6.2.1) can still continue to participate in the main study. If the subject enrolls in a clinical study with an investigational drug (including investigational vaccines), the subject will have to withdraw from the current study first.

Subjects who discontinue may withdraw consent for use of their samples for future research (refer to Section 11.7). In such a case, samples will be destroyed after they are no longer needed for the clinical study. Details of the sample retention for research are presented in the main ICF.

4.6.4 Documentation of Discontinuation of Subjects

Document the reasons for early discontinuation of any subject from the study on the appropriate case report form (CRF). If the reason for early discontinuation is an AE or an abnormal laboratory value, record the specific event or test result on the AE CRF, and monitor the subject until the event is resolved or deemed stable by the investigator.

4.7 Study Discontinuation

The Sponsor has the right to terminate this study or remove a participating site at any time. Reasons for terminating the study or site may include, but are not limited to, the following:

- The incidence or severity of AEs in this or other studies indicates a potential health hazard to subjects as described in section 4.7.1 Study Treatment Stopping Criteria.
- Subject enrollment is unsatisfactory.
- Data recording is inaccurate or incomplete.
- Investigator does not adhere to the protocol or applicable regulatory guidelines in conducting the study.
- A decision from the IRB/IEC, or regulatory authority to terminate the study.
- The Sponsor may also opt to not conduct any of Cohorts 7–15 if they are considered redundant or to otherwise not contribute to the achievement of the study's objectives.

4.7.1 Study Treatment Stopping Criteria

The occurrence of any one of the following treatment emergent events in any ongoing study using ODV at therapeutic doses:

- 2nd degree Mobitz Type 2 or 3rd degree heart block;
- drop in ejection fraction (EF) by ≥ 10 points with absolute EF $< 50\%$;
- a cardiac event that is serious, severe or life-threatening;

will lead to stop of recruitment and dosing in all subjects in the current study if adjudicated by the Sponsor, in consultation with the Investigator, to be at least possibly related to the study regimen. Such event(s) will be reported to the Sponsor medical monitor within 24 hours. Upon this notification, a safety assessment of the event by the Sponsor in consultation with the Investigator will take place within 72 hrs and the outcome of the assessment and its associated action towards the study will be reported to Health Authorities and Ethics Committees in compliance with safety reporting regulations, as applicable.

4.8 Futility Criteria

4.8.1 Predefined Criteria to Determine the Futility of an Individual Treatment Regimen

The futility of any of the regimens evaluated in the study will be assessed by the Sponsor based on predefined criteria, as detailed below. Once a predefined futility criterion is met, appropriate action will be taken by the Sponsor, which may include halting the enrollment of individual treatment arms and/or extending treatment duration of subjects who have not yet reached end of treatment at that time. Futility criteria will be in place during the entire conduct of the study. The Sponsor will evaluate the futility criteria and notify the Principal Investigator if a futility criterion is met.

The objective of the futility criteria is to detect futile regimens as early as possible and ideally within a timeframe that would allow the Sponsor to take action (i.e., while recruitment or treatment phase is ongoing). The futility criteria will take into account post-treatment failure for virologic reasons (viral relapse; see Definitions of Terms). For confirmation of viral relapse, an HCV RNA retest should be scheduled (see Sections 6.2.3 and 6.2.4). However, the Sponsor may evaluate futility criteria based on the original test results without waiting for the retest results.

The futility criteria will have been met:

- If > 2 subjects in any 1 cohort experience viral breakthrough or inadequate virologic response while recruitment is ongoing. Further recruitment in the cohort will then be discontinued
- If $\sim 15\%$ of subjects in a cohort experience relapse at any available timepoint during the follow-up phase (at 24 weeks after actual end of study drug treatment or earlier for subjects who have not yet reached the 24 weeks after actual end of study drug treatment visit).

If the futility criterion is met for a regimen evaluated in a historically easier to treat population (e.g., subjects with GT1 infection without cirrhosis), then that regimen will not be evaluated in historically more difficult to treat populations (e.g., subjects with GT1 infection and with cirrhosis).

If a drug regimen evaluating a particular treatment duration is found to be futile in a population, a shorter duration of that drug regimen will not be assessed in that population. Also, shorter duration cohorts (e.g., 6 weeks) will only be initiated if supported by viral kinetic data from longer duration cohorts in the same patient population. Supportive data are defined as viral load below the limit of quantification for $\geq 80\%$ of subjects at Week 6 in an 8-week cohort. A similar paradigm will be applied for cohorts of 4 weeks' duration based on 4-week data from cohorts of 6 weeks' duration.

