On-treatment Failure	Subjects who did not achieve SVR12 and with confirmed HCV RNA \geq LLOQ at the actual end of study drug treatment. Includes subjects: 
 • With viral breakthrough, defined as a confirmed increase of $>1 \log_{10}$ in HCV RNA from nadir, or confirmed HCV RNA of >100 IU/mL in subjects whose HCV RNA had previously been <LLOQ while on treatment. • With Inadequate virologic response defined as $<1 \log_{10}$ decline from baseline in HCV RNA after 4 weeks of treatment • Who do not experience viral breakthrough or inadequate virologic response and have confirmed HCV RNA \geqLLOQ at the actual end of study drug treatment (e.g., completed study drug treatment, discontinued due to adverse events, withdrawal of consent).
Viral Relapse	Subjects who did not achieve SVR12, with HCV RNA <LLOQ at the actual end of study drug treatment and confirmed HCV RNA \geq LLOQ during follow up.

HCV: hepatitis C virus; LLOQ: lower limit of quantitation; RNA: ribonucleic acid.

Synopsis

A Phase 2a, Open-Label Study to Evaluate the Safety, Pharmacokinetics and Efficacy of the Combination of AL-335 and Odalasvir, with or without Simeprevir, in Treatment-Naïve Subjects with Genotype 1, 2 or 3 Chronic Hepatitis C infection with or without compensated Child Pugh A Cirrhosis

[figure not shown]
Protocol No. :	AL-335-604
Phase:	2a
Study Drugs:	AL-335, Odalasvir (ODV), Simeprevir (SMV)
IND Number:	This is a non-IND study
EudraCT No.:	2016-002845-46
Background Therapy:	None
Comparator:	None
Indication:	Chronic hepatitis C (CHC)

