After the initial cohort (Cohort 1), subsequent cohorts may be enrolled concurrently or in a staggered fashion. Effective as of approval of protocol version 7, prior to evaluating a given treatment regimen in subjects with cirrhosis or for a shorter duration, efficacy, safety, and available PK data for that treatment regimen in subjects without cirrhosis and/or for a longer duration will be reviewed. Specifically, data from at least 10 subjects at the SVR4 time point will be reviewed and, if acceptable (see Section 4.8), subsequent cohorts evaluating shorter durations and/or subjects with cirrhosis will be initiated. The timing of initiating enrollment in these subsequent cohorts will be coordinated such that SVR12 data from at least 10 subjects in the earlier cohort will be available before the end of treatment visit occurs for the first subject in the subsequent cohort. This timing is designed to enable extension of the treatment duration in the subsequent cohort if the earlier cohort is determined to have insufficient efficacy.

Based on data available as of 17 February 2017, the following cohorts have been completed, initiated or are planned (Table 2-1). Available VK data are also included. Safety, viral load and PK data from dosing regimens in subjects without cirrhosis and/or dosed for longer treatment durations will be evaluated and, if they indicate an adequate safety and efficacy profile, dosing with the same regimen in cohorts with cirrhosis or for shorter treatment durations will be permitted. Cohorts 6 through 12 are currently open for enrollment or planned at the time of this protocol finalization. The cohort regimens will only change if emerging data requires they be altered for safety purposes. Some planned cohorts may not be enrolled if emerging data are not supportive or suggest the cohort is not necessary to achieve the study's objectives.

Table 2-1. Completed, Initiated, and Planned Cohorts[^] with Available VK Data

Cohort #	GT	Cirrhosis	AL-335 dose (mg)	ODV dose (mg)	SMV dose (mg)	Duration (weeks)	Cohort Status	Number (%) achieving SVR
1	1	N	400	50 QD	100	8	Through SVR24	20/20 (100%), SVR24
1b	1	N	800	50 QOD	--	8	Through SVR24	18/20 (90%), SVR24
2	1	N	800	50 QOD	75	8	Through SVR24	20/20 (100%), SVR24
3	1	N	800	50 QOD	75	6	Through SVR24	20/20 (100%), SVR24
4	1	N	800	50 QOD	--	8 (N=5) 12 (N=8)	Through SVR24 Through SVR12	3/5 (60%), SVR24 7/8 (88%), SVR12

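### The on-treatment futility criterion in Protocol 4.8.1 stops counting when a cohort closes to recruitment, so later breakthrough or inadequate response contributes nothing to the futility decision.

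*Protocol*

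**What the plan says.** Section 4.8.1 of the Protocol sets two ways to meet futility:

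- **Criterion 1, on treatment:** more than 2 subjects in any one cohort "experience viral breakthrough or inadequate virologic response while recruitment is ongoing". The stated action is to discontinue recruitment in that cohort.
- **Criterion 2, after treatment:** about 15% of "subjects in a cohort experience relapse at any available timepoint during the follow-up phase".

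The Definitions describe viral relapse as "Subjects who did not achieve SVR12, with HCV RNA <LLOQ at the actual end of study drug treatment and confirmed HCV RNA" at or above LLOQ in follow-up. Section 8.2.3 has the same end-of-treatment condition.

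On scope, 4.8.1 states: "Futility criteria will be in place during the entire conduct of the study". It gives the aim as finding futile regimens early enough to act during the recruitment or treatment phase. Extending treatment for subjects not yet at end of treatment is one of the listed actions.

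Three rules on progression follow:

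- If futility is met in an easier-to-treat population, "then that regimen will not be evaluated in historically more difficult to treat populations".
- If a duration is futile in a population, a shorter one is not assessed there.
- Shorter cohorts also need viral kinetic support: "Supportive data are defined as viral load below the limit of quantification for" at least 80% of subjects at Week 6 of an 8-week cohort.

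The Synopsis and Section 2.1 add a review of at least 10 subjects at SVR4. If the result is acceptable, with a pointer to Section 4.8, "subsequent cohorts evaluating shorter durations and/or subjects with cirrhosis will be initiated". Section 2.1 separately requires an adequate safety and efficacy profile before the same regimen is used in cirrhosis or for a shorter time.

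**The concern.** The recruitment clause sits inside criterion 1, so the count closes with enrolment. Cohorts have only 10 to 20 subjects, up to 50 sites may take part, and inadequate response cannot be judged before Week 4. If a cohort fills quickly, much of its on-treatment experience comes after the count has closed.

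Both bars on progression that rest on futility depend on a criterion being met. Section 1.7 cites 4.8.1 as the means of detecting unacceptable treatment failure early. For on-treatment failure, that assurance ends at the last enrolment, when treatment is still running and could still be acted on.

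**Working it through.** The documents give no operating characteristics for the futility rule, so there is no stated figure to reproduce.

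**Step 1. Which events count**

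| Event | Criterion 1 | Criterion 2 |
|---|---|---|
| Breakthrough or inadequate response, cohort recruiting | counts | no, if at or above LLOQ at end of treatment |
| Same event, enrolment closed | does not count | no, if at or above LLOQ at end of treatment |
| Relapse | does not count | counts |

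The second row is the gap.

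**Step 2. No time limit**

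P(3 or more of n) from Binomial(n, p), at p = 20%, 30% and 40%:

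- n = 20: 0.79, 0.96, 1.00
- n = 10: 0.32, 0.62, 0.83

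**Step 3. Rule as written, simulated**

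From the documents: cohort size and the threshold of 3 or more. Assumed: recruitment time R, failure rate p, timing of failures and result delay.

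- Entry E ~ Uniform(0, R) weeks.
- Failure ~ Bernoulli(p).
- Detection D = E + Uniform(2, 8) + 1 week.
- K = number of failures with D earlier than the last entry. The criterion fires if K is 3 or more.

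With p = 30%:

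| R (weeks) | n = 20 | n = 10 |
|---|---|---|
| 4 | about 0% | 0% |
| 6 | 2% | 0.2% |
| 8 | 15% | 2% |
| 12 | 52% | 11% |
| 16 | 70% | 20% |
| 24 | 82% | not tabulated |
| no time limit | 96% | 62% |

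Timing matters too. With R = 8 and n = 20, the 15% becomes 52% if failures arise over Weeks 2 to 4.

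**Step 4. Cross-check with a fixed lag**

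Place 20 entries evenly over A weeks and let every failure be visible L weeks after first dose. Let m be the number of subjects who reach week L before the last entry. Then P = P(Binomial(m, p) is 3 or more), at p = 20%, 30% and 40%:

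- A = 4, L = 4: m = 1, so P = 0 at any p.
- A = 8, L = 6: m = 5, giving 0.06, 0.16, 0.32.
- A = 8, L = 4: m = 10, giving 0.32, 0.62, 0.83.
- A = 24, L = 4: m = 16, giving 0.65, 0.90, 0.98.

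The direction is the same: fast accrual nearly disables the criterion and slow accrual largely restores it.

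**Step 5. Does the relapse criterion fill the gap?**

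Suppose 6 of 20 fail on treatment after enrolment closes and remain quantifiable at end of treatment. Then 20 - 6 = 14 can relapse. With no relapse, SVR is 14/20 = 70% (Clopper-Pearson 95% CI 45.7% to 88.1%) and neither criterion is met. Taking about 15% as 3 of 20, P(3 or more relapses among 14) is 0.03 at 5% relapse and 0.16 at 10%.

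**Step 6. Does the Week 6 rule fill it?**

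Partly, and only for shorter durations. Having 16 of 20 below the limit is 80% and passes, so 20 - 16 = 4 subjects can be above it. That is already more than the 2 that criterion 1 tolerates.

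**The case against.** The strongest reply has four parts.

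**Other checks exist.** A reader might infer that a regimen with many late on-treatment failures is never called futile and moves unchecked into cirrhosis. The documents do not support that. The relapse criterion can still be met. An on-treatment failure shows as non-SVR4 at the SVR4 review, and the adequate-profile condition in Section 2.1 does not refer to 4.8. SVR12 data from at least 10 subjects are also due before the first end-of-treatment visit in the next cohort, and the sponsor may drop planned cohorts. This stands. However, none of these reviews states a threshold, and the SVR4 judgement points back to the section with the gap.

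**Accrual may be slow.** A reader might infer that most on-treatment failures will surface after recruitment closes. The documents do not show it. Table 2-1 lists Cohort 6 as enrolling with 11 subjects when 10 already had SVR12 results. Eight weeks of treatment plus 12 of follow-up, less the 2-week visit window, is at least 18 weeks. At that pace the criterion had seen nearly all of its subjects. Accrual for Cohorts 1 to 3 is not shown.

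**The failure rates are hypothetical.** The four failures that Section 1.2.1.2 classifies by type, in Cohorts 1b and 4, are all relapses, which criterion 2 counts. The 30% used above has no source in the documents.

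**The two statements can be reconciled.** One criterion could act during recruitment and the other through follow-up, so that criteria of some kind are always in place. That reading is possible, but it leaves on-treatment failure without a criterion during the treatment phase in which the section says it wants to act.

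**Conclusion.** The gap is real and follows from the text alone: once enrolment closes, breakthrough and inadequate response add nothing to either criterion, contrary to the section's stated scope and aim. The bars in 4.8.1 that depend on futility are therefore not triggered by those failures. What remains is the relapse criterion, the Week 6 rule for shorter durations, and reviews without a stated threshold.

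The size cannot be fixed from the documents. With 20 subjects and the assumptions in Step 3, the chance that criterion 1 fires runs from about 0% (4 weeks' recruitment) to 82% (24 weeks), against 96% without the limit. The only accrual evidence, from Cohort 6, points to the slow end.

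The matter concerns the decision rule. On-treatment failures are SVR12 failures in the SAP, so no efficacy estimate is biased. It is worth settling while Cohorts 7 to 12 are still at screening or planned.

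**What to change.** Reconcile 4.8.1 with its own stated scope and with the Synopsis and Section 2.1:

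1. Move the recruitment clause from the criterion to its consequence. Criterion 1 would be met when more than 2 subjects in a cohort have viral breakthrough or inadequate virologic response at any time up to the end of the treatment phase. If the cohort is still recruiting, recruitment stops, as now.
2. Keep the existing events and count, and assess them in real time. Do not substitute the on-treatment failure term of Section 8.2.2. It applies only to subjects without SVR12, so it cannot be settled until 12 weeks after treatment, and it requires confirmation. For relapse, 4.8.1 already lets the sponsor evaluate futility on original results without waiting for the retest.
3. State that criterion 1 feeds both futility-based bars in 4.8.1 and the judgement of acceptability at the SVR4 review.

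Subjects who are quantifiable at end of treatment without breakthrough or inadequate response would still fall outside both criteria. The sponsor should say whether that is intended.

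The cost is a short protocol edit. No new data are needed, because Section 6.2.3 already has HCV RNA processed in real time and monitored by the sponsor. The downside is that a regimen may be called futile somewhat more often.

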5.0 DOSING REGIMEN

5.1 Rationale for Dosage Selection

5.1.1 AL-335

A dose of 400 to 1,200 mg qd for AL-335 has been selected for this study. These doses are based on safety and PK data from Study AL-335-601 (Section 1.2.1.1), Study AL-335-602 (Section 1.2.1.2), and preliminary data from Cohorts 1-3 in Study AL-335-604 (Section 1.2.1.2). In these studies, single and multiple doses up to 1,200 mg have been well tolerated and preliminary information on the impact of ODV and SMV dosing on the pharmacokinetics of AL-335 and its metabolites is known.

Evaluation of higher doses of AL-335 up to 1,200 mg qd is considered justified because:

- AL-335 and its metabolite exposures appear to increase less than dose proportionally for AL-335 doses > 800 mg
- Higher doses of AL-335 may be needed to increase antiviral activity
- It is anticipated that the 1,200 mg qd dose of AL-335, even in the setting of a drug–drug interaction with SMV and/or ODV, will deliver mean projected exposure of ALS-022227 that will not exceed the NOAEL established in nonclinical studies.
- The safety and pharmacokinetics of a dose that will deliver exposures ≤ 2 -fold those already evaluated in this and earlier studies can be safely evaluated in this study given the intensive nature of the safety/PK assessments defined in the Schedule of Events (Section 6.0).

5.1.2 Simeprevir

A dose of 75 to 150 mg for SMV has been selected for this study. In a drug-drug interaction study in healthy volunteers (AL-335-602), PK results suggest ODV increases SMV exposure (AUC) 1.8-fold. It is anticipated that the 100 mg dose of SMV, along with the interaction of ODV, will result in exposures of SMV approximately similar to 150 mg (the approved dose) without interaction; a dose that has demonstrated to be efficacious and well tolerated in patients with CHC. Similarly, it is anticipated that the 75 mg dose of SMV, along with the interaction of ODV, will result in exposures of SMV approximately similar to 100 mg (the approved dose in Japan) without interaction; this dose has also been demonstrated to be efficacious and well tolerated in patients with CHC. For a 150 mg dose of SMV, even in the setting of a drug-drug interaction with ODV, the projected SMV exposures are expected to be within the range of

exposures seen in patients with mild (Child Pugh A) cirrhosis, a population in which the 150 mg SMV dose is approved without dose adjustment.

5.1.3 Odalasvir

A daily dose of 12.5 to 50 mg for ODV has been selected for this study. In prior studies, a 50 mg daily dose of ODV given as a liquid filled capsule has been shown to be well tolerated and have clinical efficacy in combination with another nucleotide (sofosbuvir) in patients infected with HCV. Also, when a liquid filled capsule of ODV was given as monotherapy in a prior study, a single dose of 25 to 300 mg demonstrated similar antiviral effects. Taken into account these data and emerging efficacy data from Study AL-335-604, it is possible total daily doses <25 mg of ODV administered as a tablet may also be efficacious. Because only 25-mg and 50-mg ODV tablets are available for this study, dosing with 25 mg ODV qod may be administered if a decision is made to evaluate the efficacy of ODV using the equivalent of a 12.5 mg daily dose.

5.1.4 Dosing Regimens for Patients With Mild (Child Pugh A) Cirrhosis

AL-335 and its metabolites appear to have similar steady state exposures in cirrhotic vs, non-cirrhotic patients (Study AL-335-601). Furthermore the 800 mg dose of AL-335 has been well tolerated and may deliver more antiviral activity than a 400 mg dose (see Section 1.2.1.1). As a result, the AL-335 dose for the first cohort of subjects with cirrhosis will be 800 mg qd.

ODV has not been studied in CHC subjects with compensated cirrhosis; however, other drugs in the same drug class are known to have lower exposures in patients with cirrhosis compared to patients without cirrhosis. As a result, it is not expected that a 50 mg dose of ODV will deliver higher exposures in patients with vs. those without cirrhosis. Nevertheless, as a precaution, the ODV dose for the first cohort of subjects with cirrhosis will be 25 mg qd or 50 mg qod.

Because SMV is primarily cleared by the liver, the SMV dose for the first cohort of subjects with cirrhosis will be the lowest possible qd dose (75 mg).

After the safety and PK data of all 3 drugs has been evaluated in the first cohort of subjects with compensated cirrhosis, the dose limits defined in Sections 5.1.1 through 5.1.3 may then be explored if supported by emerging data.

